10.2 Safety Endpoint

10.2.1 The overall serious adverse event rate will be assessed for all patients at the stated follow-up periods. Complications associated with each of the following setting will be documented and reported separately:

10.2.2 Complications resulting from immediate IORT

10.2.3 Complications resulting from delayed IORT with or without reexcision

10.2.4 Complications resulting from WB-ERBT following WLE and immediate IORT (e.g., if lesion is > 5 cm)

10.2.5 Complications of mastectomy after initial WLE and IORT

10.3 Cosmesis Endpoint

The surgeons or radiation oncologists will evaluate cosmetic results at stated follow-up periods. Cosmetic results will be assessed using the Harvard Scale:

Excellent - The treated breast looks essentially the same as or better than the opposite breast.

Good – There are minimal but identifiable effects of radiation on the treated breast

Fair – There are significant effects of radiation on the treated breast

Poor – There are severe tissue sequelae secondary to irradiation

The appearance of the breast will be described in detail, including the presence of skin telangiectasia, skin atrophy, scarring, pigment change, erythema, fat necrosis, fibrosis, retraction or contour defect, volume loss, and other significant treatment effects. Each of these features will be documented as “none”, “present but does not affect cosmesis”, or “present and affects cosmesis”.

Digital photos of both breasts will be taken pre-treatment and at each stated follow-up period.

10.4 Quality of Life Endpoint

Patients will be asked to complete Quality of Life (QOL) questionnaires at baseline, and at the 3 month, 6 month, 1 year and 2 year follow-up point using validate QOL instruments published by the EORTC (EORTC QLQ-BR23 & QLQ-C30 version 3.). Quality of life will evaluate physical appearance and symptoms. Patients will be asked to assess differences between the treated and untreated breast and to provide an overall assessment of the appearance of the treated breast. They will also be asked to rate their breast and non-breast symptoms during the 4-week period prior to completion of each QOL questionnaire.

11.0 SPECIAL INSTRUCTIONS:

11.1 None

12.0 DATA COLLECTION AND MONITORING

FORMS TO BE USED IN THE STUDY (TO BE CREATED):

Enrollment Form (TT00)

Eligibility Worksheet Form (TT01)

Entry Form 1 (TT02)

Entry Form 2 (TT03)

Surgery Form (TT04)
Pathology On-Study Form (TT05)
Pathology Form (TT06)
Intraoperative Radiotherapy Form (TT07)
Complication Form (TT09)
Additional Procedure Form (TT10)
Photography Form (TT16)
Lost To Follow Up Form (TT17)
Cosmesis Evaluation (TT18)
Quality of Life Questionnaires EORTC QLQ-BR23 & QLQ-C30 version 3.

13.0 STATISTICAL CONSIDERATIONS

This is a pilot study to evaluate the feasibility of IORT for the treatment of patients with DCIS who undergo WLE of the breast lesion. Currently at USC, about 20% of patients who elect WLE for the treatment of DCIS are found to have surgical margins that measure less than 1mm. For these patients, reexcision (or mastectomy) is recommended unless the small distance occurs at the anterior and posterior margins if the skin has been removed anteriorly or the pectoralis muscle fascia has been removed posteriorly. Among patients requiring re-operation, it can be argued that the decision to undergo IORT was not optimal. Careful use of mammography and CE-MRI should reduce the likelihood that, based on inadequate margins, a re-operation would be necessary. In addition, for tumors that are found to be 5 cm or greater, or that have multicentric or extensive multifocal disease, in the surgical specimens, WB-EBRT is recommended. While there are studies indicating that WB-EBRT can be given safely following IORT, in this setting, the decision to treat these patients with immediate IORT was not optimal.

The primary aim (Section 2.1) of this study is to estimate the likelihood that CE-MRI and mammography were not able to identify patients for whom IORT is not optimal – because a re-operation (re-excision or mastectomy) was required. The secondary aim (Section 2.2) is to estimate the likelihood that CE-MRI and mammography were not able to identify patients for whom WB-EBRT was indicated. In addition, the safety of IORT administered at the time of initial WLE will be evaluated (Section 2.3).

An additional secondary aims, but also very important, will be to document the treatment course and complications of those patients who received delayed IORT (after initial WLE) (Section 2.4) or who received immediate IORT but subsequently required mastectomy or WB-ERT (Section 2.5).

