2.0 OBJECTIVES AND PURPOSE

In this investigation, we will determine whether or not patients with DCIS deemed eligible for “immediate” IORT based on pre-operative mammography and CE-MRI can be successfully treated with IORT without the need for additional therapy due to inadequate surgical margins or large tumor size. To accomplish these objectives, this study has several specific aims:

- 2.1 Specific Aim 1: To evaluate the ability of pre-operative mammography and CE-MRI to select suitable candidates for immediate IORT, without the need for re-excision. At USC, the re-excision rate for DCIS is about 20%, compared to published rates as high as 50%⁵⁻⁷. In this study, with the use of CE-MRI, a re-excision rate of 15% or less will be acceptable and a rate of 30% or more will be unacceptable.
- 2.2 Specific Aim 2: To evaluate the ability of pre-operative mammography and CE-MRI to select suitable candidates for immediate IORT, without the need for additional WB-EBRT.
- 2.3 Specific Aim 3: To evaluate the safety and tolerability of IORT administered at the time of initial WLE (immediate IORT).
- 2.4 Specific Aim 4: To evaluate the safety and tolerability of IORT administered at the time of re-excision in a patient who has previously undergone a lumpectomy (e.g., a patient who has inadequate margins but is still believed to be an acceptable candidate for lumpectomy and radiotherapy, or a patient who has previously undergone successful lumpectomy but who desires IORT as adjuvant radiotherapy).
- 2.5 Specific Aim 5: To evaluate the safely and tolerability of post-operative WB-EBRT or mastectomy given after initial unsuccessful IORT (e.g., a patient who initially received immediate IORT but who was subsequently found to an unsuitable candidate for IORT).

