5.3.3 Cohort 2 (Delayed IORT group)

- a. Localized DCIS measuring ≤ 4 cm or less on surgical pathology

- i. Delayed IORT could be performed for the explicit purpose of administering IORT or performed following re-excision of a previously operated breast to achieve clear surgical margins.
- ii. This cohort includes patients who were excluded from immediate IORT based on pre-operative imaging suggesting ineligibility for immediate IORT, but who are subsequently found to meet histological criteria (localized DCIS ≤ 4 cm and no invasive cancer) for IORT based on surgical pathology.
- iii. Unifocal microinvasive (T1mic or invasive focus ≤ 1 mm in maximal diameter) is allowed following initial WLE if surgical pathology margins were ≥ 2 mm for both the invasive and non-invasive components.
- iv. Delayed IORT must be performed within 3 months of initial WLE.

5.3.4 Cohort 3

- a. Subjects who received IORT at the time of initial WLE but whose surgical pathology indicates the need for further therapy:
 - i. DCIS measuring greater than 5 cm on surgical pathology.
 - b. Surgical margins width < 2 mm.

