7.0 STUDY AGENT ADMINISTRATIONS OR INTERVENTION AND TOXICITY MANAGEMENT PLAN

7.1 Patient Surgery and IORT

- 7.1.1 Each patient will undergo WLE to remove DCIS and to create a cavity. Each of the following procedures qualifies as WLE: breast conserving surgery, lumpectomy, segmental mastectomy, segmental resection, and partial mastectomy.
- 7.1.2 Recognizing the potential for DCIS to be larger than demonstrated on imaging, the surgeon will aim to excise the lesion with surgical margins of 10 mm. Multiple localizing wires will be placed pre-operatively to facilitate resection.
- 7.1.3 Due to the potential for finding occult microinvasive carcinoma in the final surgical pathology, sentinel node biopsy will be allowed at the discretion of

the surgeon.

- 7.1.4 At the conclusion of IORT, surgical clips will be placed in the resection cavity to mark the surgical margins to facilitate re-excision, if indicated.
- 7.2 Criteria for Receiving Additional therapy after IORT (Cohort 3)
 - 7.2.1 Patients with DCIS >5 cm will be advised to undergo WB-EBRT (or mastectomy) despite having received IORT, even if surgical margins are clear (\geq 2mm).
 - 7.2.2 Patients with surgical margins width of <2 mm following local excision and immediate IORT will be advised to undergo re-excision. If residual disease is found and new final margins are <2 mm, the patient will be advised to undergo WB-EBRT. However, no addition therapy will be needed if no residual disease is found, or if final margins is \geq 2mm.

7.3 Ancillary treatments.

Neoadjuvant hormonal therapy (e.g., Tamoxifen or Fulvestrant) and chemopreventive therapy (e.g., green tea extract) will be allowed provided that the total duration of neoadjuvant hormonal or chemopreventive therapy does not exceed 30 days prior to WLE and immediate IORT.

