10.0 CRITERIA FOR EVALUATION AND ENDPOINT DEFINITIONS

10.1 Feasibility Endpoint. The primary efficacy endpoint of the treatment will be re-operation (re-excision or mastectomy) rates following WLE and IORT.

Re-excision (or mastectomy) will be indicated for patients with microscopic surgical margins measuring <1 mm following WLE and immediate IORT.

Additionally, the following data will also be reported and analyzed:

10.1.1 Indications for WB-EBRT. Patients with margins that are margins < 2 mm after reexcision for <2 mm margins, or, DCIS > 5 cm.

10.1.2 Extent of disease. Extent of disease will be determined by measuring the dimensions of the DCIS lesion as demonstrated by pre-operative mammography and CE-MRI and the dimensions of the DCIS lesion contained within the surgical resection specimen

10.1.3 Surgical Margins. Surgical margins will be defined as the distance from the closest tumor cells to the cut or inked edge of the surgical specimen.

10.1.4 DCIS histopathology. DCIS histopathology will be determined by evaluating the histopathological type, grade (histological, nuclear, and mitotic), the presence or absence of comedonecrosis or invasive carcinoma in the pre-operative biopsy and the surgical specimen.

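### The indication for whole-breast radiotherapy (WB-EBRT), on which secondary Aim 2 rests, is stated one way in Sections 7.2 and 10.1.1 and another way in Section 13.0

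*Combined protocol and SAP*

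**What the plan says.** Section 2.2 sets Aim 2 as the ability of mammography and CE-MRI to pick candidates for immediate IORT "without the need for additional WB-EBRT". Section 13.0 restates it as the likelihood that the imaging studies "were not able to identify patients for whom WB-EBRT was indicated".

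The indication itself, or the need for further therapy, appears in several places:

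- Section 7.2.1: "Patients with DCIS >5 cm will be advised to undergo WB-EBRT (or mastectomy) despite having received IORT". Section 7.2.2 adds patients who have residual disease and margins still under 2 mm after re-excision.
- Section 10.1.1, under the heading for WB-EBRT indications: "Patients with margins that are margins < 2 mm after reexcision for <2 mm margins, or, DCIS > 5 cm".
- Section 13.0: WB-EBRT is recommended "for tumors that are found to be 5 cm or greater, or that have multicentric or extensive multifocal disease", judged on the surgical specimen.
- Section 5.3.4, on further therapy in Cohort 3: "DCIS measuring greater than 5 cm on surgical pathology", or a margin under 2 mm.
- Section 10.2.4 gives a lesion over 5 cm as its example of a patient receiving WB-EBRT after immediate IORT.
- Section 3.2.3 gives extensive multifocal or multicentric carcinoma as the ground on which a minority of patients will prove unsuitable for IORT. It names no other.
- Section 13.2 will summarise whether WB-EBRT was recommended, on account of margins, tumor size or any further reason.

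**The concern.** Aim 2 is a proportion whose numerator is the set of patients with WB-EBRT indicated. The protocol gives two lists for that set, and neither contains the other. Section 13.0 adds multicentric and extensive multifocal disease and includes a lesion of exactly 5 cm. Sections 7.2 and 10.1.1 include failed margins after re-excision, which the WB-EBRT sentence in 13.0 does not mention.

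The same patient can therefore be an Aim 2 failure under one section and a success under another. Because 7.2 is also the section that tells clinicians what to advise, the difference can reach the patient as well as the tabulation. Cohort 3 membership is exposed in the same way: its rationale in 3.2.3 rests on a category that its criteria in 5.3.4 do not list.

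**Working it through.** The protocol gives no target rate, power or decision rule for Aim 2, so there is no planned figure to reproduce. The check is a comparison of the lists on four specimen profiles.

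| Specimen after WLE and immediate IORT | Sections 7.2 and 10.1.1 | Section 13.0 sentence |
|---|---|---|
| Over 5 cm, clear margins | Indicated | Indicated |
| Exactly 5 cm, clear margins, neither multicentric nor extensively multifocal | Not indicated | Indicated |
| 5 cm or less, clear margins, multicentric or extensively multifocal | Not listed | Indicated |
| Under 5 cm, residual disease and margins still under 2 mm after re-excision, neither multicentric nor extensively multifocal | Indicated | Not listed |

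Three of the four profiles are classified differently. The second should be rare. The third matters most, because it is the category that 3.2.3 singles out.

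**Could the registration criteria empty the third profile?** Section 5.4.4 excludes multicentric DCIS, defined as lesions more than 3 cm apart, and 5.4.6 excludes diffuse suspicious calcifications. These apply at registration. Section 13.0 concerns what the specimen shows afterwards, and disease that imaging missed is exactly what Aim 2 is meant to count. The exclusions make the profile less common but do not remove it.

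**Would the planned data identify it?** Section 9.1 lists the specimen features to be determined: histology, lesion size, margin width and invasion. Multifocality and multicentricity are not on that list; Sections 4.2 and 4.3 record them from imaging. Extensive multifocal disease is not defined anywhere. Under 13.0, Aim 2 would depend partly on an undefined finding that is not among the listed pathology features.

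**Size.** Section 13.1.1 plans 79 patients treated with immediate IORT. The change in the Aim 2 rate for k patients classified differently in the same direction is k/79:

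- k = 1: 1/79 = 1.27 percentage points.
- k = 5: 5/79 = 6.33 percentage points.

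The documents do not give k. The range of 1 to 5 is an assumption, shown only for scale.

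**Primary design.** The two-stage rule in 13.1.1 continues if at least 19 of 25 patients need no re-excision and succeeds if at least 62 of 79 do not. With p the true chance of needing no re-excision, the probability of success is the sum over x = 19 to 25 of P(Bin(25, p) = x) × P(Bin(54, p) ≥ 62 − x). This gives 0.049 at p = 0.70 and 0.904 at p = 0.85, consistent with the stated alpha of 5% and beta of 10%. The WB-EBRT indication does not enter this calculation.

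**The case against.** The strongest reply is that Section 13.2 already settles the count. It reports whether WB-EBRT was recommended and leaves the reasons open, so a patient advised WB-EBRT for multifocal disease is counted whether or not 10.1.1 lists that reason. This stands as far as it goes, and the reason categories in 13.2 already go part of the way to a tabulation by reason. It does not reconcile the lists. A clinician who follows 7.2 has no instruction to recommend WB-EBRT to the patient in the third profile; one who follows 13.0 does. The inconsistency moves from the count to the advice, and from there back into the count.

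A second reply is that the 13.0 sentence is narrative, that endpoint definitions belong to Section 10, and that 10.1.1 and 7.2 largely agree. That is a fair description of the layout. But the sentence says what is recommended and calls immediate IORT not optimal for these patients, and the next paragraph of 13.0 states Aim 2 in terms of indication.

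A reader might also infer more than the documents support:

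- *That any small multifocal lesion with clear margins changes category.* Section 13.0 requires the multifocal disease to be extensive, or the disease to be multicentric.
- *That this category will be the main reason for Aim 2 failure.* Section 3.2.3 expects a minority of patients to be unsuitable. It does not say they will have clear margins and lesions of 5 cm or less; many might be caught by size or margins anyway.
- *That the denominator of the WB-EBRT tolerability rule in 13.1.3 is undefined.* That rule concerns WB-EBRT following IORT, so its natural denominator is patients who received it. The lists affect it only through the advice given.
- *That Section 5.3.4 is a further WB-EBRT definition.* It speaks of further therapy in general; the direct conflict is between 7.2 and 10.1.1 on one side and 13.0 on the other.

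**Conclusion.** The inconsistency is real and lies in the current text: two lists of indications for one secondary endpoint, differing at the 5 cm boundary, on multicentric and extensive multifocal disease, and on failed margins after re-excision. Each patient classified differently moves the Aim 2 rate by 1.3 points at the full 79. How many there will be is unknown. It is probably few, because such disease must escape both imaging methods and still come with clear margins and a specimen of 5 cm or less.

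It would be wrong to read this as a threat to the trial's main conclusion. The primary rule counts re-excision only, and Aim 2 is estimated without a threshold, so no decision turns on the shift. What is at stake is an interpretable secondary estimate, consistent Cohort 3 membership and consistent advice to patients. The text comparison supports this firmly; the size is illustrative.

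**What to change.** Reconcile Sections 5.3.4, 7.2, 10.1.1, 13.0 and 13.2 to one list of WB-EBRT indications covering the size cut, margin status, and whether multifocality or multicentricity counts. The investigators must choose the list; this review takes no position on which clinical criteria are right. Use it for the Aim 2 count and Cohort 3 membership, and bring the rationale in 3.2.3 into line.

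Tabulate Aim 2 failures by reason, so that the rate can be read under either list. If a multifocality or multicentricity criterion is kept, define it for the specimen and add it to the features recorded under Section 9.1.

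The cost is protocol wording, plus one item on the pathology form if that criterion stays. The sample size and the primary decision rule do not change.

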13.1 Study Design and Sample Size Justification

The study design was selected based on the primary aim: to evaluate the ability of CE-MRI and mammography to identify patients for whom IORT is not optimal because of the inability to achieve sufficiently wide surgical margins. If 15% or fewer patients require re-excision, this would be considered acceptable and encouraging for further study; however, a reexcision rate of 30% or higher would not be acceptable.

13.1.1 Accrual to Cohort 1 (Specific Aims 1-3 in Sections 2.1 – 2.3).

Patients will be enrolled in Cohort 1 until 79 patients have received immediate IORT. All patients who are deemed eligible for IORT based on mammography and CE-MRI results will be considered in the decision to stop or continue the trial. There will be one interim analysis when 25 patients have completed WLE and immediate IORT, whether or not additional therapy is needed.

After 25 patients have been evaluated, if 19 or more did NOT require re-excision (based on the surgical specimen), then accrual will continue until 79 patients undergo WLE and immediate IORT. If 7 or more of the initial 25 needed re-excision, then the study will terminate and investigators will conclude that the current method for staging is not sufficiently accurate.

After 79 patients have been evaluated, if 62 or more did NOT need re-excision (based on surgical specimen), investigators will conclude that the chance of correctly identifying a tumor that is suitable for IORT is greater than 70% and that further study of the approach would be justified. If 18 or more of the initial 79 needed re-excision, then investigators will conclude that the chances of correctly identifying a tumor that is suitable for IORT is less than 85%. In this instance, investigators would aim to improve the staging procedures before continuing with this approach.

With this Simon optimal 2-stage design, there will be a 5% chance (alpha) of incorrectly deciding that that approach warrants further study, when the true chance of correctly staging is less than 85%; and there will be a 10% chance (beta) of correctly deciding that this approach warrants further study, when the true chance of correctly staging is greater than 70%.

To evaluate the safety and tolerability of immediate IORT, the following side effects or complications will be taken as evidence that IORT was not well tolerated:

- a. any Grade 2 or greater toxicity
- b. failure for the surgical incision to heal as evidenced by wound dehiscence, wound infection, or skin ulceration.

If 25% or more of Cohort 1 patients experience the above side effects or complications, this will be considered clear evidence that IORT is not well tolerated and will lead to suspension of accrual to this cohort. The decision to continue unchanged, modify the regimen, or terminate the trial will be based on a careful review of all patients treated to date, and all toxicities and complications experienced. The rules given below will trigger such a review (and are based on the sequential probability ratio test with the theoretical parameters set to $\alpha=0.10$, $\beta=0.10$, $p_0=0.05$, $p_a=0.25$). At the completion of the study, all complications and toxicities will be summarized and reported. During the conduct of the trial, when an unacceptable toxicity or complication (as defined above) is observed, the number of patients (X) who

have experienced any unacceptable toxicity or complication will be compared to the number of patients (N) who have begun IORT in this Cohort. If the number of patients, N, is greater than Nx, the number given in the bottom row of the Table 1, then accrual will continue. If N is less than or equal to Nx, then accrual will be suspended for review of the data.

Table 1: Criteria for Suspending Accrual to Evaluate Tolerability											
X: # pts with unacceptable toxicity or a complication	2	3	4	5	6	7	8	9	10	11	12
N _x : Suspend trial if # patients (N) is \leq N _x	≤ 6	≤ 1	≤ 2	≤ 2	≤ 3	≤ 4	≤ 5	≤ 6	≤ 6	≤ 7	≤ 7
	4	1	9	7	5	3	0	8	6	6	9

These rules were selected to ensure a reasonable chance that the trial would not be suspended if the true chance of unacceptable toxicity were less than 5% and a reasonable chance that it would be suspended if the true chance were 25% to 30% (Table 2). The table below summarizes these probabilities. The values in the table below are based on 10,000 simulations and are accurate to ± 0.01 (based on a 95% confidence interval).

Table 2.							
True Chance of Unacceptable Toxicity or Complication		5%	10%	15%	20%	25%	30%
Probability of Suspending Accrual to Review Tolerability		0.07	0.37	0.78	0.96	0.99	0.99

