13.1.3 Accrual to Cohort 3 (Specific Aim 5 in Section 2.5)

Cohort 3 will be a subset of patients who begin in Cohort 1 (i.e. are deemed candidates for immediate IORT and who receive immediate IORT) but who subsequently are found to require a mastectomy, re-excision alone, re-excision followed by WB-EBRT, or WB-EBRT alone. This cohort will be followed to monitor and document the complications of the mastectomy and WB-EBRT (with or without re-excision) which are performed following IORT. If all 79 patients are enrolled in Cohort 1 (i.e. the study is not stopped early), then we would expect between 8 and 17 patients requiring an additional surgical procedure (mastectomy or re-excision); as soon as 18 patients require an additional surgical procedure, the study will be terminated.

Using the same definition of unacceptable toxicity as above in 13.1.1 for Cohort 1 and in 13.1.2 for Cohort 2 (any Grade 2 or greater toxicity, or failure for the surgical incision to heal as evidenced by wound dehiscence,

wound infection, or skin ulceration), the rules in Table 3 will also be applied to the patients undergoing an additional surgical procedure in Cohort 3. Separately, we will evaluate the tolerability of WB-EBRT following IORT, in the same manner (using Table 3). Unacceptable toxicity of WB-EBRT include any Grade 2 or greater toxicity, skin flap necrosis, skin ulceration, wound dehiscence, or brachial plexopathy.

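### The first-stage re-excision limit is read only after 25 patients, although the seventh event already settles it; stopping at that event would spare some women IORT at no cost in alpha or power

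*Combined protocol and SAP*

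**What the plan says.** Section 13.1 sets the two rates behind the design: "If 15% or fewer patients require re-excision, this would be considered acceptable", while "a reexcision rate of 30% or higher would not be acceptable". Section 13.1.1 then gives a two-stage rule for Cohort 1:

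- **Timing of the first stage:** "There will be one interim analysis when 25 patients have completed WLE and immediate IORT, whether or not additional therapy is needed".
- **Go:** 19 or more of 25 without re-excision, judged once 25 have been evaluated; accrual then runs to 79.
- **Stop:** "If 7 or more of the initial 25 needed re-excision, then the study will terminate", with the conclusion that the staging method is not accurate enough.
- **Final judgement:** after 79 patients, 62 or more without re-excision is success and 18 or more re-excised is failure.

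Section 13.1.3 handles the overall limit differently: "as soon as 18 patients require an additional surgical procedure, the study will be terminated". The toxicity rules in 13.1.1 and 13.1.2 are also checked each time an event occurs.

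**The concern.** Events accumulate and cannot be undone. Once seven of the first 25 women need re-excision, no later result can bring the count back to 19 successes. Section 13.1.3 acts on that logic at the 18th event, but 13.1.1 provides no stop or pause at the seventh. Of the re-excision and toxicity limits in 13.1, the first-stage re-excision limit is the only one without an event-triggered stop.

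Women enrolled between the seventh event and the 25th patient would receive single-dose IORT before their margins are known, when their results can no longer alter the go/no-go decision. Section 1.2.2 describes the cost of IORT given in the wrong patient: possible re-operation or added WB-EBRT, repeat IORT generally not permitted, and no published data for IORT in DCIS. The question is how many women this involves, and whether stopping sooner would cost anything statistically.

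**Working it through.** **Inputs.** From 13.1 and 13.1.1: unacceptable re-excision rate 30% (success rate 0.70), acceptable rate 15% (success rate 0.85), first stage 25 patients with at least 19 successes to continue, total 79 with at least 62 successes to conclude in favour. From 13.0: a current local rate of about 20% for margins under 1 mm, used as a sensitivity value. The 40% rate is an added sensitivity value. Pathology delay is not given, so it is varied as an assumption.

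**Step 1: reproduce the design.** With X1 ~ Bin(25, p) and X2 ~ Bin(54, p) successes,

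P(success) = Σ over k = 19 to 25 of P(X1 = k) · P(X2 ≥ 62 − k).

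- p = 0.70: 0.0492 (alpha)
- p = 0.85: 0.9041 (power, so beta 0.0959)

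An exhaustive search at alpha ≤ 0.05 and beta ≤ 0.10 returns these same boundaries as the Simon optimal design. (The wording of 13.1.1 attaches alpha to 85% and beta to 70%; the figures reproduce the other way round. That is a separate matter.)

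**Step 2: the seventh event decides.** 25 − 7 = 18, which is below 19. Stopping at the seventh event therefore gives the same go/no-go outcome in every possible sequence of results, so alpha and power do not move.

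**Step 3: how many women are treated after that point.** Let q be the true re-excision rate and T the patient number of the seventh event:

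P(T = t) = C(t − 1, 6) · q^7 · (1 − q)^(t − 7), for t = 7 to 25.

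P(stop) = Σ P(T = t). Women treated afterwards, over all trials = Σ (25 − t) · P(T = t). Dividing by P(stop) gives the figure per stopped trial. With no pathology delay:

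| True rate q | P(stop at stage 1) | Mean T, given stop | Women after, per stopped trial | Women after, over all trials |
|---|---|---|---|---|
| 15% | 0.070 | 21.5 | 3.5 | 0.24 |
| 20% | 0.220 | 20.9 | 4.1 | 0.9 |
| 30% | 0.659 | 19.1 | 5.9 | 3.9 |
| 40% | 0.926 | 16.6 | 8.4 | 7.8 |

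At 30%, the seventh event comes before patient 25 in 93% of stopped trials. Expected sample size falls from 25 + (1 − 0.659) × 54 = 43.4 to 43.4 − 3.9 = 39.5. With the 18-event stop of 13.1.3 also applied, it is 35.5.

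**Step 4: pathology delay (assumption).** If L more women are treated before the seventh event is confirmed, replace 25 − t by max(0, 25 − t − L). Per stopped trial:

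- 30%: 4.1 (L = 2) or 2.7 (L = 4)
- 20%: 2.5 (L = 2) or 1.4 (L = 4)

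**Step 5: how many of these women would need re-excision.** Outcomes after the seventh event are independent of its timing, so at 30% the number is 0.30 × 5.9 ≈ 1.8 per stopped trial; the other 4.1 would not.

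**Step 6: effect on the estimate.** At a true 30%, given a first-stage stop, the naive rate averages 0.351 if all 25 are observed and 0.385 if accrual stops at the seventh event (mean of 7/T). Both exceed 0.30; curtailment adds 0.034.

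**The case against.** A single look after the first-stage patients is how a Simon design ordinarily runs. The boundaries are right, and curtailment is an optional refinement. The stop sentence does not itself forbid acting at the seventh event, although the one interim analysis is the only timing supplied. This stands: nothing is miscalculated.

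The exposure is also modest if imaging works as hoped: 0.9 women over all trials at 20% and 0.24 at 15%. A seventh event by patient 15 has probability only 0.13 at 30% and 0.02 at 20%. Delay shrinks the saving further, and the extra women would add some Cohort 3 data. These limits stand too, but the saving stays above zero in every case examined.

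Two stronger readings are tempting, and the documents support neither:

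- **That the later women would all be wrongly selected.** At a first-stage stop, 13.1.1 faults the staging method, not each patient. At 30%, about 1.8 of the 5.9 would need re-excision.
- **That stopping would spare them re-excision or radiotherapy.** Re-excision follows inadequate WLE margins, a risk they would also face off study, and section 1.1 gives WB-EBRT as the usual treatment after WLE. Under 7.2.2, re-excision that reaches 2 mm or more calls for no further therapy. What is avoided is narrower: IORT under a selection method already judged inadequate, followed in a minority by re-operation or WB-EBRT.

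The estimation cost is real, because the primary aim in 13.0 is worded as estimation. The 18-event stop already accepts a cost of the same kind.

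**Conclusion.** The point holds as a cheap improvement in exposure and internal consistency. Section 13.1.1 ties the first-stage limit to 25 completed patients, the seventh event makes the go criterion unreachable, and 13.1.3 already uses an immediate stop for the other re-excision limit.

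The saving depends on the true rate, ranging from 0.24 women over all trials at 15% to 7.8 at 40%, and per stopped trial from 3.5 to 8.4. These are upper bounds, because they assume that margin results are known before the next patient is treated. They also assume independent patients with a constant re-excision rate. That the error rates are unchanged depends on neither assumption, since no decision changes.

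**What to change.** In 13.1.1, state that accrual to Cohort 1 ends once the seventh qualifying event among the first 25 patients is confirmed. Keep the 19-of-25 go rule, and cross-refer to the 18-event stop in 13.1.3 so that both limits run continuously.

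Define one counted event for both limits, because a stop that fires on a single event needs it. Section 13.1.1 counts re-excision, while 13.1.3 counts mastectomy or re-excision. The margin that triggers re-operation also differs: under 1 mm in 10.1, under 2 mm in 5.3.4 and 7.2.2. These passages must be reconciled; which threshold applies is for the investigators.

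Add to 13.2 that, after a first-stage stop, the reported re-excision rate will use an estimate and interval that allow for curtailed sampling.

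**Cost.** A few sentences, with no change to thresholds, sample size, alpha or power. Margin width is already measured for every specimen (9.1, 9.3), but results must be reviewed as they arrive. A stopped trial will rest on fewer patients, with a naive rate biased further upward (0.385 against 0.351 at a true 30%).
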